Statistical blinding will be assured to generate summary variables and set the final analysis for between group differences. Once the final statistical coding is defined and validated by the TSC, the true group identity will be revealed and additional descriptive information on treatment will be provided.

- Coding allocation to random A, B to blind first step of statistical analysis
- Treatment description included in separate dataset to be coded with different IDS than main dataset.

5. Outcome measures

Primary Outcome measure

Crying time diary

The main outcome is daily crying time in minutes. This can be measured for crying times from the first day after treatment to the thirteenth day after treatment. Daily crying time is obtained by adding hourly reported crying times from 6AM to 5:59AM the next day. D-1 is computed from the hourly reported crying time on the day prior to the treatment if the entire day is completed. When incomplete, it is replaced by the parent reported 24h baseline crying time (castor.csv). Daily crying time is considered as missing if any of the time hour slots has missing values within the day.

The primary outcome is the between group average difference in crying time from day 1 after the treatment to day 13 after the treatment. Repeated measures random linear mixed effect adjusting for baseline crying time, expectations for treatment outcome and infant's age is used to estimate the between group difference.

If diaries only report the presence of crying during each hour slot, then each time slot is replaced by the corresponding median reported crying time for infants that were crying during that hour on that specific day of follow-up.

Secondary Outcome measure

Parent Confidence

Changes of parent confidence will be measured using the Parent Confidence Score at baseline and 14 day follow up. This score relies on 15 questions about parenting confidence with a likert scale of 4 choices (0 to 45 points). Changes over time will be measured at an individual level by adding the baseline value as a dependant variable in the mixed effect model. Movement of 6 points or more is to be considered as meaningful.

Global change

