- Analyse potential correlations between missing data in diary and overall summary measures.

Missing data for hourly entries will not be replaced (e.i. not missing total at random) unless parents did not report minutes in an explicit was. Graphical representations are replaced by estimates of hourly crying time. Reported crying within a hourly time slot without specification on the duration is replaced by the median observed crying time from other reported crying for that specific time slot (i.e. hour of the day and day of the trial).

Given the nature of the analysis, missing data within the diary will only reduce the power but should not affect the overall analysis.

For a diary to be considered, at least 7/14 days need to be filled in. Furthermore, best-case, and worst-case scenario will be simulated for the primary outcome implementing lowest and highest values for missing data (see sensitivity analysis).

Descriptive analysis

Descriptive statistics will be used to summarise the characteristics of participants in each arm of the trial. This will include baseline values, treatment schedules, compliance and follow-up. We will show number and percentage or mean and standard deviation for categorical and normally distributed continuous variables respectively. For data severely deviating from a normal distribution, we will present median and interquartile ranges. Probability of observed between groups difference will be provided using either Fisher's exact test, Chi2 test, and or Student's t-test.

Primary outcome analysis

We will analyse the primary outcome of crying time (e.i. individual daily measures of mean crying time in minutes) using random-effects multilevel linear regression. Crying time will be entered as the response variable (dependant) and the link function is identity. Therefore, lack of independence for measures from the same participant will be accounted for. To improve statistical power, the following explanatory variables are to be added to improve the modelling of the between-group differences

- baseline crying time (continuous),
- expectations from treatment (ordinal)
- and age of infants at entry (continuous).

To account for missing data, the data can be categorized and treated as nominal.

Results will be reported as between group difference in crying time in minutes with a 95% confidence interval. Statistical inference for significance of effects of the intervention will be calculated using Wald Chi² test.

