Checking assumptions for primary outcome

a) Assumptions for repeated measures random linear mixed effect

The following assumptions for repeated measures random linear mixed effect need to be tested:

- The explanatory variables are related linearly to the response.
- The errors have constant variance.
- The errors are independent.
- The errors are normally distributed.

A graphical representation will plot the residuals against group allocation. This can indicate if the model fits the data appropriately. The residuals will also be plotted in the order of days after treatment to see any indications of visible trend over time. The residuals will be plotted against the fitted values to test whether there is any non-constant error variance. Finally, a histogram with a normal probability plot and Wilk-Shapiro test will be used to test the assumption of normality for crying-time distribution in each group.

If the distribution of crying time is not Gaussian, then it will be categorised, and the distribution of the response variable will be considered as ordinal, and the link function is logit. When the assumptions for distribution of the residuals are not met, transformation is to be used to make the analysis possible.

b) Testing and accounting for trends over time

Three methods are used to investigate trend over time:

- a. Visual and statistical assessment of trend over time is to be made using fractional polynomials in regression analysis separately for each group.
- b. Repeated measures random linear mixed model is to be used to test interactions between group allocation and days of follow-up. This makes it possible to assess that group differences are constant through time. Explanatory variables are group allocation, interaction between group allocation and number of days of follow-up, baseline crying time day before treatment, infant age at entry, treatment expectations. Linearity of response for the explanatory variable is tested as trends over time using mixed regression analysis.
- c. Day to day means in each group will be calculated using Delta-method linear prediction with fixed portion. Furthermore, linear trend over time will be tested in each group by modelling day to day residuals within the model.

Assumptions are to be verified on the linearity of the progression through time. Transformation is to be used if linearity is not met.

Secondary outcomes analysis

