* Adjusted for baseline crying time, infant age and prior expectations for osteopathic care

Table 3 Effects of treatment on other outcomes including undesirable events

| Outcomes | Test group (TTR) | Control group (GTR) | Between group difference* |
|--|---------------------|------------------------|------------------------------|
| | N=xx | N= xx | (CI 95%; P-value) |
| Parenting Confidence Score [0–45]; mean (SD) | | | |
| Perceived changes in symptoms; n(%) | | | |
| Completely recovered | | | |
| Much improved | | | |
| Slightly improved | | | |
| No change | | | |
| Slightly worse | | | |
| Much worse | | | |
| Vastly worse | | | |
| Weight changes over 14 days (kg); mean (SD) | | | |
| Satisfaction with received care; n (%) | | | |
| Very satisfied | | | |
| Fairly satisfied | | | |
| Neither satisfied nor dissatisfied | | | |
| Fairly dissatisfied | | | |
| Very dissatisfied | | | |
| Unexpected reactions; n(%) | | | |
| More distress | | | |
| Crying more | | | |
| More unsettled | | | |
| Vomiting more | | | |
| Increased feeding difficulties | | | |
| Increased difficulties sleeping | | | |
| Other | | | |
| Serious adverse events; n(%) | | | |
| Death | | | |
| Hospitalisation | | | |
| Long lasting morbidity | | | |
| Any | | | |

* P-values measured using likelihood ratio test in linear/logistic regression, Mann-Whitney U test for ordinal outcomes, Chi2 for categorical

Table 4 Number of sessions, advice given, additional treatment and effectiveness of blinding

| | Test group (TTR) N=xx | Control group (GTR) N= xx | Between group difference* |
|--|---------------------------|---------------------------------|------------------------------|
| | Mean (SD) | Mean (SD) | (CI 95%; P-value) |
| Number of sessions; mean (SD) | | | |
| Advices; n(%) | | | |
| Managing the baby's sleep pattern | | | |
| Managing the baby's feeding pattern | | | |
| Mother's diet | | | |
| Handling the baby | | | |
| Managing the baby's environment | | | |
| Parenting behaviour | | | |
| Reassure parent/guardian | | | |
| Other | | | |
| Medication and remedies; n(%) | | | |
| Prescribed medication | | | |
| Anti-gas drops | | | |
| Herbal supplements | | | |
| Probiotics | | | |
| Non-cow or anti-allergenic formula milk | | | |
| Omeprazol | | | |
| Other | | | |
| Additional care; n(%) | | | |
| General practitioner | | | |
| Accident and Emergency | | | |
| Unplanned hospital admission | | | |
| Another osteopath | | | |
| Paediatrician | | | |

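### The primary model has no term for day of follow-up, so the statement that missing diary days only cost power is not justified

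*SAP*

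**What the plan says.** The primary outcome in SAP section 5 is the average between-group difference over days 1 to 13 after treatment. The model is specified in three places:

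- Section 5, Primary Outcome measure: a repeated-measures mixed model "adjusting for baseline crying time, expectations for treatment outcome and infant's age is used to estimate the between group difference".
- Section 8, Primary outcome analysis: the same three covariates in a random-effects linear regression.
- Section 9, footnote to Table 2: "Adjusted for baseline crying time, infant age and prior expectations for osteopathic care".

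Day of follow-up is in none of them. It appears in section 8, Checking assumptions, part (b), where a separate model includes the "interaction between group allocation and number of days of follow-up" to see whether the group difference is constant.

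On missing data, section 5 treats a whole day as missing if any hour is blank. Section 8 accepts a diary with 7 of 14 days filled in. It then states, without condition: "Given the nature of the analysis, missing data within the diary will only reduce the power but should not affect the overall analysis".

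**The concern.** A mixed model copes with days that are missing at random provided its model for the mean is right. Without day, the model treats every recorded day of an infant as an equally good reading of that infant's 13-day level. An infant whose diary stops on day 7 then contributes the average of days 1–7 as if it were the average of days 1–13.

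This matters if crying changes over those days. The SAP does not say that it falls, but three of its statements point that way: entry requires more than 3 hours a day (section 1), the expected mean during follow-up is 120 minutes (section 7), and the condition is described as self-limiting (section 1).

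What is at stake is the primary estimate itself, in two situations:

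1. The timing of missing days differs between arms. The arm with more early-ending diaries then appears to cry more.
2. The treatment effect changes over time and late days are missing, even equally in both arms. The estimate is then pulled toward the early effect.

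**Working it through.** **The plan's own figure.** Section 7 gives a 30-minute difference, SD 45, 90% power and two-sided 5%: n = 2 × (1.960 + 1.282)² × 45² / 30² = 47.3, so 48 per arm. This reproduces, and 48 per arm is used below.

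**Assumptions not in the SAP.**
- Between-infant SD 43 and within-infant SD 45. These agree with the SAP's SD of 45 for the infant mean: √(43² + 45²/13) = 44.8.
- Short diaries end on day 7.
- A linear fall of 3 to 8.6 min/day. The upper value is (180 − 120)/7, taking the entry threshold as the starting level and 120 as the mid-point value.

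**Weights.** In a random-intercept model an infant with n recorded days has weight w(n) = n / (45² + n × 43²).
- w(13) = 13/26,062 and w(7) = 7/14,968, a ratio of 0.938.
- If a share p of an arm's diaries is short, their share of the weight is f(p) = 0.938p / (1 − p + 0.938p).

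**Situation 1: true effect zero, parallel fall, short diaries in 10% vs 30%.** The mean day is 4 for days 1–7 and 7 for days 1–13, a gap of 3 days.
- f(0.10) = 0.094 and f(0.30) = 0.287, a difference of 0.192.
- Bias = 3 × slope × 0.192.

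| Fall (min/day) | Bias without day (min) | Bias with day (min) |
|---|---|---|
| 3 | 1.7 | 0 |
| 5 | 2.9 | 0 |
| 8.6 | 5.0 | 0 |

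A simulation of 300 trials (fall 5 min/day, 0% vs 30% short) gave 4.5 minutes without day, against 4.3 by formula, and 0.2 with a linear day term (Monte Carlo SE 0.5).

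In the same set-up, equal shares (30% in each arm) gave no bias. Days missing at scattered times (5% vs 30%) gave −0.7 without day and −0.6 with it (Monte Carlo SE 0.5), so no detectable bias.

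**Situation 2: effect growing linearly from 0 on day 1 to 60 on day 13, equal shares of short diaries.** The true average is 30; the average over days 1–7 is 15. The planned model gives 30 − 15 × f(p).

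| Short diaries, both arms | Planned model | Day only | Day + group × day, equal-weight average |
|---|---|---|---|
| 15% | 27.9 | 27.9 | 30.0 |
| 20% | 27.2 | 27.2 | 30.0 |
| 40% | 24.2 | 24.2 | 30.0 |

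**Precision.** With complete diaries the SE is 44.8 × √(2/48) = 9.14 under all three models. With 40% short diaries it is 9.26 for the planned model and 9.33 for the full one.

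**The case against.** **What stands.**
- The fall in crying is inferred, and its slope is assumed. An early drop followed by a plateau fits the same SAP figures with much less slope later on.
- Parents are blinded and the control arm receives equal time, so nothing in the SAP suggests that diaries stop earlier in one arm. A 10% vs 30% split is a threefold imbalance.
- The biases are small beside the 30-minute target and an SE of about 9.
- The SAP looks at the issue indirectly. It compares missingness between arms, tests group by day, and reports each day's difference in Table 2, so a building effect would be visible.

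**What does not remove the point.** The trend checks lead at most to a transformation, not to a change in the primary estimate. The best- and worst-case scenario reruns the same primary analysis, with 25th or 75th percentiles that are not said to be day-specific.

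**Stronger readings that a reader might infer.**
- *The SAP contradicts itself by calling the gaps not random.* The phrase "Missing data for hourly entries will not be replaced (e.i. not missing total at random" explains why hourly gaps are not imputed. Data that are not missing completely at random can still be missing at random, so there is no contradiction.
- *The missing day term costs much power.* A simulated contrast of 77% against 93% needs 40% short diaries and an effect growing from 0 to 60; the SAP's only dropout figure is 15%. Day alone does not change that estimate.
- *The false-positive rate clearly rises.* A simulated 13% against 7% (300 trials) is partly noise. A bias of 5.0 with SE 9.14 is a shift of 0.55 SE, which implies about 8.5%.
- *Day was agreed and then dropped.* The version history mentions it, but that log describes superseded text and is no evidence of an error.

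**Conclusion.** The point holds in a limited form. As specified, the primary model does not support an unconditional statement that missing diary days only reduce power, and no other part of the SAP repairs this.

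Under the stated assumptions the primary difference can be off by about 1.7 to 5 minutes when early-ending diaries are unequal between arms (10% vs 30%), or by about 2 to 3 minutes of a 30-minute average when the effect grows and 15–20% of diaries stop early in both arms. Slopes, SDs and shares of short diaries are assumptions, apart from the agreement of the SDs with the SAP's 45.

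The documents do not show that the result will be biased. With complete diaries, or with equal timing and parallel trends, it is not. The change is worth making because it is nearly free, not because the expected error is large.

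**What to change.** 1. In section 5, in section 8 (Primary outcome analysis) and in the Table 2 footnote, add day of follow-up (13 levels) and group × day as fixed effects. Define the primary estimate as the equal-weight average of the 13 day-specific differences. Day alone removes only the bias from unequal timing. Table 2 already asks for adjusted differences on each day, so the day-specific estimates are needed in any case.
2. Replace the sentence in section 8 (Missing data) with the assumption made: days are missing at random given arm, day, covariates and the infant's recorded days.

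**Cost.** There are 12 + 12 = 24 extra fixed-effect parameters, against 96 × 13 = 1,248 daily records if diaries are complete, plus one post-estimation contrast. The SE does not change with complete diaries and rises from 9.26 to 9.33 with 40% short diaries. The change does not cure days missing not at random, so the planned best- and worst-case analysis is still needed.

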This question asks about overall change in the infant's symptoms, from completely recovered to vastly worse. (Completely recovered, much improved, slightly improved, no change, slightly worse, much worse, vastly worse). These levels are coded numerically in an ordinal manner and are to be compared between groups using non-parametrical approaches.

Experience and satisfaction

Experience was measured using a 5-point likert scale from Very good, fairly good, neither good not bad, fairly poor and very poor.

Satisfaction was measured using a 5-point likert scale from Very satisfied, fairly satisfied, neither satisfied nor dissatisfied, fairly dissatisfied and very dissatisfied.

We also asked if the parent thought osteopathic care helped their baby using a yes, no or unsure response.

Unexpected and or Adverse events

We asked parents about additional care they may have administered to their infants and additional health care consultations they sought during the trial period as a proxy indicator of adverse events, and we also asked directly about any changes in symptoms that cause the parent concern. These included more distress, more crying, more unsettled, more vomiting, increased difficulty in feeding, sleeping and anything else (other).

Serious adverse events are reported by parents and managing osteopaths. These are assessed by the trial managing group and coded as for the reason for being a SAE and the estimated likelihood these are related to the treatment.

6. Randomisation

Block randomisation with variable block size of 4 and 6 generated by CastorEDC.

7. Sample size

From data collected during the pilot phase (n=13), we confirmed crying times as expected by Wolke et al. We estimate the average daily crying time over the two-week follow-up period to be of 120 minutes with a SD of 45 minutes. To detect a minimum of 30 minutes additional reduction in crying time between the intervention and control group with 90% power and a two-sided 5% significance level we would need 48 infants in each arm of the trial. If we allow for a 15% drop out we would need to randomise 112 infants, 66 in each arm of the trial. This sample size calculation is conservative because it disregards the fact that there are repeated measures in each infant and that the model will be corrected for the baseline crying time value. Thus, the actual power will be higher.

| Power | MCID (daily reduction in crying time in minutes) | | | |

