|--------------|---|-----------|-----------|-----------|
| | 10 | 15 | 30 | 60 |
| 0.8 | 636 | 284 | 72 | 18 |
| 0.9 | 852 | 380 | 96 | 24 |
| 0.95 | 1054 | 468 | 118 | 30 |

Table 4 : Sample size estimates without loss to follow up.

8. Statistical Analysis

All analysis will be intent-to-treat except for a secondary per protocol analysis on the primary outcome. All *P* values will be two sided, and the significance level is set at 5%. We will use STATA15 to precode the entire analysis prior to data collection (.do file). Deviations from the initial statistical plan will be recorded on the statistical output report.

Computing new variables

Protocol deviation

A new variable will be computed to identify deviations from protocol. Any participant who dropped-out, missed out a planned treatment, received external osteopathic care during the follow-up, or did not complete the diary daily are considered as participants who deviated from the protocol.

Unexpected reactions and adverse events

Serious adverse events, sae, will be reported as a total number for each group and as a risk ratio.

Serious adverse events will be monitored throughout the trial and reported by either the osteopaths or the participant parent.

Detailed reporting of unexpected reactions from follow-up and from the follow-up questionnaire are to be summarised to describe the presence of any unexpected reactions during the follow-up period.

Treatment description

A new set of variables is to be merged from detailed description of treatments during each visit and summarize whether each subset of care was provided or not.

Parent confidence scale

Parent confidence scale at baseline (pcs_b) and at 14 days (pcs_e) are computed from the 15 individual questions. Likert scales are scored 0 to 3 points. Scores for Q13 are inverted. Values for not applicable in Q1 and Q9 are given the score of 2. The points are then added up.

For descriptive purposes, the parent confidence scale at baseline can be compared with the following ranges:

- Non-clinical range 40 or more
- Mild clinical range 36-39
- Moderate clinical range 31-35
- Severe clinical range 31 or less

Missing data

Where participants withdraw, we will compare the characteristics of those withdrawing against those who remain in the study. Furthermore, we will do an:

- overall descriptive analysis of missing data searching for patterns,
- compare between group differences in missing data,

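### Minor: the primary test uses a large-sample Wald chi-square reference with no denominator degrees of freedom and no stated estimator (ML or REML); at about 96 infants its true size is about 5.3% under REML and 6.0 to 6.5% under ML

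*SAP*

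**What the plan says.** All from the SAP.

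- **Model** (section 8, Primary outcome analysis): daily crying time is analysed "using random-effects multilevel linear regression" with an identity link. Repeated measures on one infant are accounted for. The covariates are baseline crying time (continuous), expectation of treatment (ordinal) and infant age (continuous). To handle missing data, variables may instead be categorised and treated as nominal. The castor.csv table in section 3 gives expectation six codes, one of them for missing.
- **Test** (same section): "Statistical inference for significance of effects of the intervention will be calculated using Wald" chi-square test.
- **Interval** (same section): "Results will be reported as between group difference in crying time in minutes with a 95% confidence interval". Its construction is not given.
- **Level** (section 8, opening paragraph): P "values will be two sided, and the significance level is set at 5" per cent.
- **Size** (section 7): "with 90% power and a two-sided 5% significance level we would need 48 infants in each arm of the trial".

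The SAP names neither ML nor REML, no denominator degrees of freedom and no small-sample correction. Section 8 (Checking assumptions) adds a fallback: if crying time is not Gaussian, it is categorised and analysed as ordinal with a logit link.

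**The concern.** Allocation is a between-infant factor. Its standard error depends mainly on the between-infant variance, which is estimated from about 96 infants after 5 to 9 fixed effects have been fitted. A Wald chi-square test treats that variance as known: it compares the estimate with a normal critical value of 1.960 where a t value on about 90 degrees of freedom would be more accurate.

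The unstated estimator adds a second effect. ML does not correct the between-infant variance for the fixed effects and understates it by a factor of roughly (n − p)/n. REML makes that correction.

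Both effects run in one direction, towards a smaller P-value and, if the interval uses the same reference, a narrower interval. At stake is how closely the primary test keeps its stated two-sided 5% level.

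**Working it through.** **1. The plan's own figure.** Inputs from section 7: difference 30 minutes ("To detect a minimum of 30 minutes additional reduction in crying time between the intervention and control group"), SD 45 minutes ("to be of 120 minutes with a SD of 45 minutes"), 90% power, two-sided 5%.

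n per arm = 2 × (1.960 + 1.282)² × 45² / 30² = 47.3, rounded up to 48. This reproduces the stated 48, or 96 in total. Power at 48 per arm on the normal reference is 90.4%.

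**2. Number of fixed effects, p.**
- Expectation as one linear score: intercept, group, baseline, age, expectation = 5.
- Expectation as six nominal levels: 4 + 5 = 9. This needs every level, including missing, to be populated.

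**3. True size of the test.** With complete diaries and a random intercept, the group test equals a regression on infant means with df = n − p.
- REML with a normal reference: size = 2 × P(t_df > 1.960).
- ML with a normal reference: size = 2 × P(t_df > 1.960 × √(df/n)).
- Width ratio against the t interval: 1.960 / t_crit under REML, and 1.960 × √(df/n) / t_crit under ML.

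Worked case, n = 96, p = 9: df = 87 and √(87/96) = 0.952. The ML cut-off on the t scale is 1.960 × 0.952 = 1.866, so size = 2 × P(t_87 > 1.866) = 6.54%.

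| Infants | p | df | t critical | REML size | REML width ratio | ML size | ML width ratio |
|---|---|---|---|---|---|---|---|
| 96 | 5 | 91 | 1.986 | 5.31% | 0.987 | 5.95% | 0.961 |
| 96 | 9 | 87 | 1.988 | 5.32% | 0.986 | 6.54% | 0.939 |
| 112 | 5 | 107 | 1.982 | 5.26% | 0.989 | 5.81% | 0.966 |
| 112 | 9 | 103 | 1.983 | 5.27% | 0.988 | 6.30% | 0.948 |

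The 112 rows assume that no infant is lost.

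**4. Incomplete diaries.** Random-intercept models were simulated with 7 to 13 observed days per infant and 6,000 runs per case. The between-infant SD of 40 and within-infant SD of 50 are assumptions. The Monte Carlo standard error is about √(0.05 × 0.95 / 6000) = 0.28 percentage points. For 96 infants:
- REML with normal reference: 5.3% (p = 5) and 5.4% (p = 9).
- ML with normal reference: 6.0% and 6.4%.
- REML with t reference: 5.0% in both.

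**5. What this means in minutes and P-values.** Unadjusted standard error at 48 per arm: 45 × √(2/48) = 9.19 minutes. Half-width on the normal reference: 1.960 × 9.19 = 18.00 minutes. On t with 91 df: 1.986 × 9.19 = 18.25 minutes. The gap is about 0.25 minutes against a 30-minute target.

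The results that would change side of 5% are those with a reported P between about 0.047 and 0.050 under REML. Under ML the lower end is about 0.041 (p = 5) or 0.037 (p = 9).

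**6. Power on the t reference.** In the simple two-sample design with 94 df, power at 48 per arm is 89.8%, and 49 per arm would be needed for 90%.

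**The case against.** The strongest objection is size. A Wald test with 96 independent units and 5 to 9 coefficients is conventional, and on its own the reference distribution costs 0.3 percentage points and a quarter of a minute of half-width. That stands, and it is why this is a minor point.

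The larger figures need an ML fit, which the SAP does not state. That also stands. However, REML cannot be presumed either. The footnotes to provisional Tables 3 and 4 take P-values from likelihood ratio tests in linear and logistic regression, and a likelihood ratio test of a fixed effect needs ML. This shows likelihood-based inference elsewhere in the plan; it does not establish how the primary model is fitted.

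Nine fixed effects is an upper case, because expectation is listed as ordinal and nominal coding is only permitted.

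Three stronger readings might be inferred and are not supported:
- **That daily records are treated as independent.** The SAP says within-infant dependence is accounted for, and the random-effects standard error already reflects between-infant variance.
- **That the 95% interval is known to be too narrow.** Only the significance test is tied to Wald. A shared reference is likely, since otherwise test and interval could disagree, but it is inferred.
- **That the test has no degrees of freedom at all.** The chi-square test of group has one; what is absent is a denominator value.

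Finally, deleting the Wald sentence outright would leave the ordinal-logit fallback without a named test. That stands and shapes the fix.

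**Conclusion.** The point holds as a low-severity, inexpensive improvement. At the planned 96 analysed infants the true size is about 5.3% if REML is used and about 6.0 to 6.5% if ML is used. An interval on the same reference would be about 1.3% too narrow in the first case and 4 to 6% in the second.

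These figures assume normal errors, a random intercept, between-infant covariates and 5 to 9 fixed effects. The simulation with partly filled diaries gives nearly the same values.

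A reader might conclude that the primary analysis fails to control its 5% level. The document does not support that: under REML the departure is negligible, and under ML, which the SAP neither states nor excludes, it is 1 to 1.5 percentage points. What is worth closing is the unstated choice of estimator, because that choice makes most of the difference.

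**What to change.** In section 8, Primary outcome analysis:
- State that the linear mixed model is fitted by REML.
- Base both the P-value and the 95% confidence interval for the group effect on a t reference with Kenward-Roger or Satterthwaite degrees of freedom, naming one of the two.
- Keep the Wald chi-square test only for the ordinal-logit fallback under Checking assumptions, where those degrees-of-freedom methods do not apply.
- Use the same settings in the sensitivity analyses that refit the linear model, since some add covariates.

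The cost is one estimation option in the analysis code and one or two sentences. P-values and intervals become very slightly less favourable: power at 48 per arm is about 89.8% instead of 90.4%. The sample size need not change for this reason.
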